## **7 TOXICITIES AND DOSEAGE MODIFICATION**

This study will utilize the CTCAE (NCI Common Terminology Criteria for Adverse Events) Version 4.03 for adverse event and serious adverse event reporting. A copy of the CTCAE Version 4.03 can be downloaded at <http://safetyprofiler-ctep.nci.nih.gov/CTC/CTC.aspx>.

### **7.1 Dose Modifications Radium Ra 223 Dichloride**

Every effort should be made to administer the full dosing regimen of Radium Ra 223 dichloride. Adjustment of dose level is not permitted.

Study visits during the treatment period should occur at 4 weeks intervals (within a window of  $\pm$  7 days). If a patient requires a toxicity related dose delay of more than 9 weeks between 2 injections, then the patient must be discontinued from the study. If patients have a radium cycle delayed, the study visits will continue per the calendar and the dose will be missed. Dosing delays may be instituted under the following circumstances:

#### **7.1.1 Myelosuppression**

Treatment-related changes in hematology parameters may occur. Results from the CBC must be reviewed prior to drug administration on Day 1. The

following parameters must be met for the patient to proceed with treatment: platelets  $\geq 50 \times 10^9/L$ , ANC  $\geq 1.0 \times 10^9/L$  and hemoglobin  $\geq 8 \text{ g/dL}$ .

- If a patient experiences CTCAE v4.03 Grade 3 or 4 neutropenia, thrombocytopenia, or anemia the administration of study drug should be delayed until recovery to Grade 2 or better.
- If a patient experiences CTCAE v4.03 Grade 3 or 4 neutropenia, thrombocytopenia, or anemia lasting  $> 14$  days, further study drug administrations must be discontinued.
- Blood transfusion is acceptable between study drug administrations but not within 4 weeks prior to the start of Radium treatment. Use of biologic response modifiers, such as G-CSF or GM-CSF, is allowed in the management of acute toxicity. After the appropriate dose modification for acute toxicity, G-CSF or GM-CSF may be used prophylactically for subsequent study treatments per institutional standard of care.

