### ***Bone Marrow Suppression***

In the randomized trial, 2% of patients on the Radium Ra 223 dichloride arm experienced bone marrow failure or ongoing pancytopenia compared to no patients treated with placebo. There were two deaths due to bone marrow failure and for 7 of 13 patients treated with Radium Ra 223 dichloride, bone marrow failure was ongoing at the time of death. Among the 13 patients who experienced bone marrow failure, 54% required blood transfusions. Four percent (4%) of patients on the Radium Ra 223 dichloride arm and 2% on the placebo arm permanently discontinued therapy due to bone marrow suppression.

In the randomized trial, deaths related to vascular hemorrhage in association with myelosuppression were observed in 1% of Radium Ra 223 dichloride-treated patients compared to 0.3% of patients treated with placebo. The incidence of infection-related deaths (2%), serious infections (10%), and febrile neutropenia (< 1%) were similar for patients treated with Radium Ra 223 dichloride and placebo.

Myelosuppression; notably thrombocytopenia, neutropenia, pancytopenia, and leukopenia; has been reported in patients treated with Radium Ra 223 dichloride. In the randomized trial, complete blood counts (CBCs) were obtained every 4 weeks prior to each dose and the nadir CBCs and times of recovery were not well characterized. In a separate single-dose phase 1 study of Radium Ra 223 dichloride, neutrophil and platelet count nadirs occurred 2 to 3 weeks after Radium Ra 223 dichloride administration at doses that were

up to 1 to 5 times the recommended dose, and most patients recovered approximately 6 to 8 weeks after administration.

In the radium-223 arm of the Phase 3 clinical trial reported in Parker et al. (2013), 12.7% (76 / 600) of subjects had grade 3+ anemia, 6.5% (39 / 600) of subjects had grade 3+ thrombocytopenia, and 2.2% (13 / 600) of subjects had grade 3+ neutropenia.

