## 6 TREATMENT PLAN

### 6.1 Administration Schedule

1 cycle = 28 days

Repeat for a total of 6 cycles

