## 8 STUDY CALENDAR

1 cycle = 28 days

- 1 ALL Pre-study / Screening procedures should be completed within 4 weeks of study enrollment - with the exception of laboratory tests which need to be completed within 2 weeks prior to study enrollment.
- 2 Hematology includes CBC with differential and platelets. CBC must be completed within 2 weeks of study enrollment and prior to treatment ( $\pm$  7 days) on day 1 of each cycle.
- 3 Chemistry includes Albumin, Alkaline Phosphatase, Aspartate Aminotransferase, Alanine Aminotransferase, Total Bilirubin, Calcium, Carbon Dioxide, Creatinine, Chloride, Glucose, Potassium, Protein, Sodium, and Urea Nitrogen.
- 4 Bone alkaline phosphatase (BAP) should be done every four weeks until the end of treatment visit or disease progression (whichever comes earlier).
- 5 PSA is required within 28 days at screening, on day 1 of each cycle and at the end of treatment visit. PSA laboratory assessments should be performed every 4 – 6 weeks after the end of treatment visit until disease progression, or the start of another treatment.
- 6 CT and bone scans should be conducted at screening, end of cycle 3 (prior to C4D1 treatment), and at the end of treatment visit (4 weeks post last treatment). Follow-up scans will be performed as clinically indicated until documented PD per treating clinician or until the start of another treatment. Scans should include CT scan of abdomen and pelvis. Imaging of the chest is only required if clinically indicated.
- 7 Bone markers collected at baseline (C1D1), C3D1, C5D1, EOT and at disease progression (whichever comes earlier); to include procollagen Type 1 intact N-terminal Propeptide (NTP) and resorption (N-telopeptide [NT], C-Telopeptide beta-cross linked [CTB] and pyridinoline).
- 8 Radium Ra 223 dichloride 55 kBq/kg\*\* on day 1 of every cycle for up to 6 cycles (\*\* 50 kBq/kg prior to implementation of the NIST update).
- 9 Enzalutamide 160 mg daily.
- 10 End of Treatment visit should be conducted 4 weeks post C6D1.
- 11 For all patients who receive study treatment, follow-up for survival will occur approximately every 8 weeks following end of treatment or as clinically indicated for up to 2 years post enrollment or death.
- 12 All procedures for day 1 of each treatment cycle have a  $\pm$  7 day window.
- 13 Subjects receiving concomitant medication with warfarin should have INR monitored more frequently as clinically indicated.

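### The rule that stops radium after more than 14 days of grade 3-4 cytopenia cannot be reliably applied from required blood counts that are nominally 28 days apart

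*Combined protocol and SAP*

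**What the plan says.** Section 7.1.1 has two rules for grade 3 or 4 neutropenia, thrombocytopenia or anemia. The next administration "should be delayed until recovery to Grade 2 or better". If the cytopenia lasts more than 14 "days, further study drug administrations must be discontinued". The same section ties the review of counts to dosing: "Results from the CBC must be reviewed prior to drug administration on Day 1".

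Section 8, note 2, sets the timing of the counts: "CBC must be completed within 2 weeks of study enrollment and prior to treatment" on day 1 of each cycle, with a window of plus or minus 7 days. Section 6.1 fixes "1 cycle = 28 days", and section 7.1 repeats the spacing: "Study visits during the treatment period should occur at 4 weeks intervals". For a dose that cannot be given, section 7.1 says: "If patients have a radium cycle delayed, the study visits will continue per the calendar and the dose will be missed".

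Three other places bear on the point:
- Section 9.3 allows more frequent safety evaluations when clinically indicated or at the investigator's discretion.
- Section 13.4.1 asks for the duration of each adverse event and follow-up to resolution, at each visit or more often if needed.
- Section 3.1.4 (Bone Marrow Suppression) reports that 4-weekly counts in the earlier randomized trial left nadirs and recovery times poorly described. It adds that in a single-dose study neutrophil and platelet nadirs came 2 to 3 weeks after injection and "most patients recovered approximately 6 to 8 weeks after administration".

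**The concern.** The stopping rule is mandatory and depends on elapsed time, but the required counts are spaced at twice the limit being judged. A patient followed exactly as written has a low count on Day 1, misses that dose, and is next counted at the following Day 1. If that count is grade 2 or better, the delay rule is satisfied and radium may be given. Nothing required by the protocol shows whether the 14-day rule was already met.

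Two patients with the same course can therefore be handled differently because one had an unscheduled count and the other did not. What is at stake is the number of injections given and the safety of patients whom the rule was written to protect.

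**Working it through.** The plan states no figure on this point, so there is none to reproduce. The check is on timing.

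**Inputs.** Limit: more than 14 days (7.1.1). Cycle: 28 days (6.1). Window: plus or minus 7 days (7.1; section 8, notes 2 and 12). Nadir on days 14-21 and recovery on days 42-56 after injection (3.1.4). Maximum gap between injections: 9 weeks (7.1, 6.6). Benchmark for any grade 3+ anemia, thrombocytopenia or neutropenia: 21%, with 35 patients (10.1.3).

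**Step 1. Gap between required counts.** Nominal 28 days; shortest 28 − 7 − 7 = 14; longest 28 + 7 + 7 = 42.

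**Step 2. What the required counts can show, at nominal spacing.**
- Low, then low: at least 28 days if the cytopenia was continuous. The rule is triggered.
- Low, then clear: the time remaining after the first low count lies anywhere between 0 and 28 days, so the 14-day limit cannot be judged.
- One low count between two clear ones: total duration is anything from just above 0 to just under 28 + 28 = 56 days.

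**Step 3. By length of episode.** Assume an episode of D days with onset uniform over a 28-day gap. The probability that no required count falls inside is max(0, 1 − D/28). The probability that two or more do is min(1, max(0, D/28 − 1)). The last column is a simulation in which each visit moves independently by up to 7 days. It gives the share of episodes whose low counts are more than 14 days apart.

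| D (days) | No count inside | Two or more inside | Shown as >14 days, with windows |
|---|---|---|---|
| 15 | 46% | 0% | 0% |
| 21 | 25% | 0% | 1% |
| 28 | 0% | 0% | 9% |
| 35 | 0% | 25% | 26% |
| 42 | 0% | 50% | 50% |
| 56 | 0% | 100% | 91% |

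At nominal spacing no episode of 15 to 28 days can be shown to exceed the limit. At 35 days three quarters still cannot.

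**Step 4. An illustration from section 3.1.4.** Suppose counts are at grade 3-4 from day 14-21 until day 42-56. This is an assumption, because the section gives nadir and recovery times and not time at grade 3-4. The episode lasts between 42 − 21 = 21 and 56 − 14 = 42 days, so the rule is met. The day-28 count is low and the dose is missed. The day-56 count is clear and radium may be given. The injections are 56 days, or 8 weeks, apart, so the 9-week limit does not catch the case.

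**Step 5. Size.** Let R be the duration remaining after the first low Day 1 count, assumed exponential with mean m. The unresolved share is P(14 < R ≤ 28) = e^(−14/m) − e^(−28/m).
- m = 14: 0.368 − 0.135 = 0.23.
- m = 28: 0.607 − 0.368 = 0.24.
- Any m: with x = e^(−14/m) the share is x − x², which cannot exceed 0.25.

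Patients expected with any grade 3+ event at the benchmark: 0.21 × 35 = 7.35. Unresolved: 7.35 × 0.23 = 1.7 to 7.35 × 0.24 = 1.8, and at most 7.35 × 0.25 = 1.8.

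**The case against.** The strongest reply is that the protocol does ask for what is needed. A grade 3-4 cytopenia is an adverse event. Section 13.4.1 wants its duration and follow-up to resolution, section 9.3 permits extra evaluations, and section 3.1.4 calls for close monitoring of patients with compromised marrow reserve. This stands in part: the intent to measure duration is there, and a careful investigator would often repeat the count. But none of these sections sets an interval or refers to the 14-day rule, so whether a mandatory rule is triggered still depends on discretionary testing.

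It can also be said that every injection must still pass the Day 1 thresholds of 7.1.1, so no patient is dosed with counts below them. That is true and limits the harm, but the 14-day rule is written as a further condition. A recovery by 6 to 8 weeks would also satisfy the recovery limit in section 3.1.4. Whether re-dosing breaches the plan therefore depends partly on which limit governs, and the passages have to be reconciled together.

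The calendar grid is missing from the text reviewed, so a mid-cycle count cannot be fully excluded. No readable text mentions one.

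A reader might infer three stronger things that the documents do not support:
- **That the rule can never be applied.** Two consecutive low counts do trigger it if the episode is continuous, and the windows sometimes bring counts closer together.
- **That re-dosing distorts the hematologic safety test.** Section 10.1.3 counts patients with one or more grade 3+ events. Anyone who could trigger the 14-day rule is already counted.
- **That about 7 of 35 patients are affected, or that all episodes outlast 14 days.** The 7 is everyone expected to have any grade 3+ cytopenia. The second claim rests on the assumption in the illustration, which uses neutrophil and platelet data from a single-dose study at 1 to 5 times the recommended dose. Those data do not cover anemia, which is 12.7 of the 12.7 + 6.5 + 2.2 = 21.4 percentage points behind the benchmark.

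**Conclusion.** The concern holds as a mismatch between a stated rule and the stated schedule. Followed as written, the protocol cannot reliably identify patients whose grade 3-4 cytopenia lasted more than 14 days. Some of them may be dosed again after a clear count about 28 days later. The gap is widest for episodes of 15 to 28 days and remains for many up to 56 days.

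The number affected is small and uncertain: about 23-24% of episodes, or at most about 2 of 35 combination patients. That rests on three assumptions: exponential remaining duration with mean 14 to 28 days, which has no source in the documents; duration measured from the first low count; and the 21% benchmark. The benchmark adds three event rates, so it may count some patients twice. Episodes after the last injection do not matter here and reduce the figure further. A different distribution of durations would change the share.

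The consequence is for injections received and patient safety. The conclusion of the 10.1.3 test does not move.

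**What to change.** Reconcile 7.1.1 with section 8, note 2, and in the same edit with the recovery limit in section 3.1.4 and the missed-dose and 9-week provisions in 7.1. There are two ways to do it:
- Note 2 requires repeat counts after any grade 3-4 result, timed so that whatever limit 7.1.1 states can be evaluated.
- 7.1.1 states its limit in terms of the counts that the calendar already schedules.

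Which limit applies is for the investigators to decide; this review proposes none.

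The cost is one calendar note or one sentence. If repeat counts are chosen, expect one or two extra routine counts in a few patients. Flag those counts as unscheduled, so that first events are still ascertained on the 4-weekly schedule that the benchmark trial used.

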### **7.1.2 Gastrointestinal events**

Diarrhea should be treated as per local practice. For Grade 3 or 4 diarrhea, a further dose of study medication should not be given before diarrhea is recovered to CTCAE v4.03 Grade 2 or baseline levels.

Nausea or vomiting should be treated as per local practice. For Grade 3 nausea or grade 3 or 4 vomiting, a further dose of study medication should not be given before nausea or vomiting is recovered to CTCAE v.4.03 Grade 2 or baseline levels.

### **7.1.3 Spinal Cord Compression**

If the patient experiences spinal cord compression during the treatment period, the patient should be treated for the event, and may receive further study drug administration if adequately recovered.

### **7.1.4 Surgical Intervention**

If surgery is required, the patient should continue with study treatment, if this is considered safe in the treating Investigator's opinion. The surgeon needs to be notified that the patient has been given radioactive drug, and needs to follow the guidelines for radioactive protection.

### **7.1.5 Non-pathological fractures**

For traumatic fractures in weight-bearing bones during treatment phase, the study drug administration should be delayed for 2-4 weeks from the time of fracture.

### **7.1.6 Pathological fractures**

Pathological fractures may occur as the result of either progressive disease or increased physical activity associated with significant pain palliation. Pathologic fractures are to be treated in a manner that attempts to maintain the best functional status and quality of life. Study treatment may continue as planned.

### **7.1.7 Any Other Toxicity**

If a subject experiences any non-hematological CTCAE v4.03 Grade 4 toxicity, attributable to the study drugs, lasting more than 7 days despite adequate treatment, further study drug administration must be discontinued.

## **7.2 Dose Modifications Enzalutamide**

Patients who experience a Grade 3 or greater toxicity attributed to enzalutamide, which cannot be ameliorated by the use of adequate medical intervention, may have their drug treatment interrupted for 1 week or until the toxicity grade improves to Grade 2 or lower severity. Enzalutamide may then be restarted at the same or a reduced dose (120 mg then 80 mg).

## 8 STUDY CALENDAR

1 cycle = 28 days

- 1 ALL Pre-study / Screening procedures should be completed within 4 weeks of study enrollment - with the exception of laboratory tests which need to be completed within 2 weeks prior to study enrollment.
- 2 Hematology includes CBC with differential and platelets. CBC must be completed within 2 weeks of study enrollment and prior to treatment ( $\pm$  7 days) on day 1 of each cycle.
- 3 Chemistry includes Albumin, Alkaline Phosphatase, Aspartate Aminotransferase, Alanine Aminotransferase, Total Bilirubin, Calcium, Carbon Dioxide, Creatinine, Chloride, Glucose, Potassium, Protein, Sodium, and Urea Nitrogen.
- 4 Bone alkaline phosphatase (BAP) should be done every four weeks until the end of treatment visit or disease progression (whichever comes earlier).
- 5 PSA is required within 28 days at screening, on day 1 of each cycle and at the end of treatment visit. PSA laboratory assessments should be performed every 4 – 6 weeks after the end of treatment visit until disease progression, or the start of another treatment.
- 6 CT and bone scans should be conducted at screening, end of cycle 3 (prior to C4D1 treatment), and at the end of treatment visit (4 weeks post last treatment). Follow-up scans will be performed as clinically indicated until documented PD per treating clinician or until the start of another treatment. Scans should include CT scan of abdomen and pelvis. Imaging of the chest is only required if clinically indicated.
- 7 Bone markers collected at baseline (C1D1), C3D1, C5D1, EOT and at disease progression (whichever comes earlier); to include procollagen Type 1 intact N-terminal Propeptide (NTP) and resorption (N-telopeptide [NT], C-Telopeptide beta-cross linked [CTB] and pyridinoline).
- 8 Radium Ra 223 dichloride 55 kBq/kg\*\* on day 1 of every cycle for up to 6 cycles (\*\* 50 kBq/kg prior to implementation of the NIST update).
- 9 Enzalutamide 160 mg daily.
- 10 End of Treatment visit should be conducted 4 weeks post C6D1.
- 11 For all patients who receive study treatment, follow-up for survival will occur approximately every 8 weeks following end of treatment or as clinically indicated for up to 2 years post enrollment or death.
- 12 All procedures for day 1 of each treatment cycle have a  $\pm$  7 day window.
- 13 Subjects receiving concomitant medication with warfarin should have INR monitored more frequently as clinically indicated.
- 14 If the physical exam, ECOG score, and vital signs are done within 28 days of C1D1 they do not need to be repeated at this time-point.

## **9 CRITERIA FOR EVALUATION AND ENDPOINT**

### **9.1 Assessment of bone metabolism:**

Serum will be collected at various time points (at baseline and during protocol treatment). Markers of bone formation (C-terminal collagen propeptide, CICP and bone alkaline phosphatase, BAP) and resorption (N-telopeptide, pyridinoline) will be analyzed using standard technical methods at the ARUP lab at the University of Utah.

### **9.2 Assessment of clinical outcomes:**

Clinical outcomes (time to PSA progression, time to first skeletal event, opioid usage, overall survival) will be assessed at various time points from the start of protocol treatment. Patients will be followed for a total of two years from the day of start of protocol treatment

### **9.3 Safety**

All subjects who receive at least one dose of study treatment will be valid for the safety analysis.

All observations pertinent to the safety of the study treatment will be recorded and included in the final report.

All AEs whether considered drug-related or not, will be reported with a diagnosis, start / stop dates, action taken, whether treatment was discontinued, any corrective measures taken, outcome, and other possible causes. For all events, the relationship to treatment and the intensity of the event will be determined by the investigator.

This trial will use the NCI-CTCAE v4.03 criteria for assessment of toxicity and SAE reporting with regard to toxicity grade.

Safety variables may include but not limited to the following: laboratory changes (complete blood counts, electrolytes, chemistry, and coagulation), changes in vital signs (blood pressure, heart rate, respiratory rate, and temperature), ECG, and, in some instances, changes in chest x-ray images, as produced at the investigator's discretion (e.g., for evaluation for pneumonia).

Routine safety and tolerability will be evaluated from the results of reported signs and symptoms, scheduled physical examinations, vital sign measurements, and clinical laboratory test results. More frequent safety evaluations may be performed if clinically indicated or at the discretion of the investigator.

### **Physical Examination**

Complete and symptom-directed physical examinations will be performed by a licensed physician (or physician's assistant or nurse practitioner).

### **Vital Signs**

Vital signs (blood pressure, respiratory rate, pulse rate and temperature) will be obtained in the sitting position. Patients should be sitting for 3-5 minutes prior to

obtaining vital signs. Weight will be taken at the start of each cycle while the patient is on Radium Ra 223 dichloride.

### **Safety Laboratory Determinations**

Laboratory evaluations will be performed as noted in the calendar.

#### **9.3.1 Interim Analysis for Safety**

There will be no formal interim analysis of the efficacy data.

An interim analysis of the safety data will be conducted during the study. The interim analysis will be conducted when 10 subjects have completed treatment with 6 injections of radium-223 dichloride or discontinued study treatment early. The purpose of this interim analysis is to formally review safety data and to assess whether it is acceptable to continue enrollment of subjects. The review of the safety data in this interim analysis will be conducted by the HCI Data Safety Review Committee (DSMC). A proportion of subjects with grade 3 or higher hematologic adverse events significantly more than those reported for the radium-223 arm of the Phase 3 trial would be evidence of unacceptable toxicity. In particular, four or more grade 3+ anemias, three or more grade 3+ thrombocytopenias, or three or more grade 3+ neutropenias in ten subjects would be statistically significantly higher than expected (at the one-sided 0.05 significance level). An adjustment may be made to these numbers if the proportion of patients with prior chemotherapy is higher than the 59% reported in Parker et al (2013).

A final safety analysis will be conducted when all 35 evaluable subjects have completed 6 doses of treatment, plus the end of treatment visit (30 days post-last dose), or discontinued treatment early.

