### **13.3 Data and Safety Monitoring Plan**

A Data and Safety Monitoring Committee (DSMC) is established at Huntsman Cancer Institute (HCI) and approved by the NCI to assure the well-being of patients enrolled on Investigator Initiated Trials that do not have an outside monitoring review. Roles and responsibilities of the DSMC are set forth in the NCI approved plan. The activities of this committee include a quarterly review of adverse events including SAEs, important medical events, significant revisions or amendments to the protocol, and approval of cohort/dose escalations. If the DSMC and/or the PI have concerns about unexpected safety issues, the study will be stopped and will not be resumed until the issues are resolved. The DSMC also reviews and approves audit reports generated by the Research Compliance Office.

All **phase II** studies are reviewed by the full committee at each quarterly DSMC meeting. This includes a review of all serious adverse events (SAEs) occurring in patients treated at HCI or its affiliates as well as all grade 3 or greater toxicities for patients on treatment and within 30 day follow-up window (only if possibly, probably or definitely related).

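### The interim safety trigger does not provide for patients who miss a radium dose and finish treatment, and its limits are read only once

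*Combined protocol and SAP*

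**What the plan says.** Section 9.3.1 (Interim Analysis for Safety) ties one look to a condition: "The interim analysis will be conducted when 10 subjects have completed treatment with 6 injections of radium-223 dichloride or discontinued study treatment early". Its stated purpose is to judge whether enrollment may continue. The limits are "four or more grade 3+ anemias, three or more grade 3+ thrombocytopenias, or three or more grade 3+ neutropenias in ten subjects", described as significantly above the phase 3 rates "at the one-sided 0.05 significance level". No pause in enrollment is stated. The final safety analysis is worded in the same way: "A final safety analysis will be conducted when all 35 evaluable subjects have completed 6 doses of treatment", plus the end-of-treatment visit, or have stopped early.

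Sections 6.6 and 7.1 deal with delays: "If patients have a radium cycle delayed, the study visits will continue per the calendar and the dose will be missed". Section 6.6 withdraws a patient when more than 9 weeks pass between two injections. Section 7.1.1 delays dosing for grade 3 or 4 neutropenia, thrombocytopenia or anemia, and discontinues study drug if the cytopenia lasts more than 14 days. Sections 7.1.2 and 7.1.5 list gastrointestinal events and traumatic fractures as further reasons for delay.

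Section 13.3 adds a quarterly review by the full DSMC. It covers all serious adverse events, and grade 3 or higher toxicities "only if possibly, probably or definitely related".

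**The concern.** Two features weaken the look.

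The first is who makes up the ten. The trigger recognizes six injections or early discontinuation. The dosing rules create a third outcome, treatment completed with fewer than six injections. Since the monitored cytopenias are one cause of that outcome, a literal reading tends to remove patients with events and fill their places with later patients.

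The second is when the limits apply. Each limit is a count among ten patients, so once it is reached nothing later can undo it. The plan still waits for the scheduled look, and enrollment goes on meanwhile.

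Safety is a primary objective (Section 1.1.2), and this is the only enrollment decision in the plan that has numeric limits.

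**Working it through.** **1. The plan's limits.** The reference rates are in Section 3.1.4 (Bone Marrow Suppression): "12.7% (76 / 600) of subjects had grade 3+ anemia, 6.5% (39 / 600) of subjects had grade 3+ thrombocytopenia". The neutropenia rate given there is 13/600, or 2.2%. Exact binomial tails with n = 10:

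- Anemia: P(X ≥ 4 | 76/600) = 0.029 (3 of 10 gives 0.123).
- Thrombocytopenia: P(X ≥ 3 | 39/600) = 0.023 (2 of 10 gives 0.134).
- Neutropenia: P(X ≥ 3 | 13/600) = 0.001 (2 of 10 already gives 0.019).

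All three limits are below 0.05, as stated. The neutropenia limit is stricter than that level requires.

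**2. Who fits neither condition.** Injections are 4 weeks apart. One missed dose leaves a nominal gap of 8 weeks, under the 9-week limit, so the patient stays on and finishes cycle 6 with five injections. Two consecutive misses leave a nominal 12 weeks, which means withdrawal, and he is counted. Cytopenia lasting over 14 days means discontinuation, and he is counted. The gap is therefore the patient with an isolated miss who resumes. One such patient among the 35 is enough to make the literal condition for the final analysis unattainable.

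**3. Possible size of the selection.** Let p be the true grade 3+ anemia rate and q the share of affected patients who miss a dose, resume and go uncounted. Unaffected patients are taken as all counted. The rate among those counted is p(1 − q)/(1 − pq). The documents give neither p nor q for the combination, so both are assumptions.

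| p | q | Rate among counted | P(X ≥ 4 of 10) |
|---|---|---|---|
| 0.40 | 0 | 0.400 | 0.62 |
| 0.40 | 0.10 | 0.36/0.96 = 0.375 | 0.55 |
| 0.40 | 0.25 | 0.30/0.90 = 0.333 | 0.44 |
| 0.40 | 0.50 | 0.20/0.80 = 0.250 | 0.22 |
| 0.30 | 0 | 0.300 | 0.35 |
| 0.30 | 0.10 | 0.27/0.97 = 0.278 | 0.29 |
| 0.30 | 0.25 | 0.225/0.925 = 0.243 | 0.21 |
| 0.30 | 0.50 | 0.15/0.85 = 0.176 | 0.08 |

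If unaffected patients also miss doses and drop out of the count, the differences shrink.

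**4. When the look falls.** Inputs: 47 patients (Section 4.2) in 18 months (Section 4.4), the first 8 all on radium (Section 4.1), then 27 of 39 (Section 10, Randomization), and 28-day cycles (Section 6.1).

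- Accrual: 47/18 = 2.61 per month. The eighth patient enters at 8/2.61 = 3.06 months.
- Radium accrual after that: 2.61 × 27/39 = 1.81 per month. The tenth radium patient enters at 3.06 + 2/1.81 = 4.17 months.
- Sixth injection at day 140 (4.60 months): look at month 8.8, with 8 + (8.77 − 3.06) × 1.81 = 18.3 radium patients enrolled.
- End of cycle 6 at day 168 (5.52 months): look at month 9.7, with 20.0 enrolled.
- Accrual over 36 months instead: 14.2 and 15.0 enrolled.

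**5. Lag between a crossed limit and the look.** I simulated 40,000 trials with exponential gaps between patients at these rates. Anemia occurred in each of the first ten with probability p, spread evenly over the visits at days 28 to 140. Results are means over trials that reach the fourth event.

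- p = 0.40: lag 2.7 months, and 4.9 further radium patients start. Timed to day 168 with six visits: 3.0 months and 5.4 patients.
- p = 0.30: 2.4 months and 4.4 patients.
- p = 0.40 with accrual over 36 months: 4.0 months and 3.7 patients.

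**6. Effect of a running count.** Among a fixed ten the count never falls. Reaching 4 at some point is therefore the same event as having at least 4 at the end, and the crossing probability is unchanged (0.029 for anemia at the reference rate).

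**The case against.** The quoted sentence says when the look happens, not whose events count. Sections 9.3, 10 (Analysis sets) and 10.1 put everyone with at least one dose in the safety population and use it for all safety analyses. Nothing says that the events of a five-injection patient are disregarded. This stands: the omission is a literal reading, not a stated rule. But those sections do not say which patients form the ten, so the ambiguity remains.

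A reader might infer that every patient who misses a dose is lost, typically because of cytopenia. The documents do not support that. Prolonged cytopenia and consecutive misses lead to discontinuation, the ±7-day visit window can absorb short holds, an event first seen after the sixth injection cannot cause a miss, and there are other listed causes of delay.

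A reader might also infer that a crossed limit necessarily goes unaddressed for months. Quarterly DSMC review, with power to stop the study, could act within about one such interval. It mitigates only in part: it has no numeric limits, its stopping clause is worded for unexpected issues, and non-serious grade 3+ events reach it only if judged related. The phase 3 rates in Section 3.1.4 are given without any attribution filter.

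Finally, a single look after full exposure is a legitimate design, and 15 or more radium patients remain to be enrolled when it occurs.

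**Conclusion.** The concern holds in a limited form. Section 9.3.1 and Sections 6.6 and 7.1 do not fit together for patients who complete treatment with fewer than six injections, and the resulting gap is related to the event being monitored. Its size cannot be derived from the documents. The fall from 62% to 22% needs both a 40% anemia rate and half of affected patients missing a dose and resuming; at a 10% share the figure is 55%.

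The timing point rests on planned accrual and evenly spread events. The limits are read at about month 9 to 10, with about 18 to 20 of 35 radium patients enrolled, or about 14 to 15 if accrual takes twice as long. So it cannot be said without qualification that more than half have entered. At 30% to 40% anemia, the decision comes about 2 to 3 months after the limit is reached, and about 4 to 5 more radium patients start in that time.

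A reader might conclude that the interim cannot serve its purpose, or that the 13-of-35 criterion fails as protection. Neither follows. The limits are correctly calculated and a substantial part of enrollment still lies ahead, and Section 10.1.3 presents 13 of 35 as a final test, not a stopping limit. This should be fixed, but it does not invalidate the safety plan.

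**What to change.** In Section 9.3.1:

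1. Reconcile the trigger with Sections 6.6 and 7.1. Define the ten as the first ten patients given at least one radium injection, each followed to the end of the treatment period or discontinuation, whatever the number of injections. Word the final safety analysis to match.
2. Keep a running tally of grade 3+ anemia, thrombocytopenia and neutropenia in these patients, stated explicitly to be regardless of attribution.
3. Notify the DSMC, for its decision on enrollment, as soon as an interim limit is reached among the ten. Keep the scheduled look.

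Running the 13-of-35 criterion as a continuous limit is optional and not part of this change.

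The cost is protocol wording, a tally and an occasional unscheduled DSMC review. No patients, tests or dosing rules change, and for the fixed ten the chance of crossing a limit stays the same. If the treatment period is taken to end at the end-of-treatment visit, the scheduled look moves about four weeks beyond the sixth injection; immediate notification offsets this.
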